## Scientific Background

Having and maintaining close social bonds is so fundamental to health, well-being, and normal functioning that bonding has been referred to as a basic need, much like the need for food and water (Baumeister & Leary, 1995). In fact, being deprived of care and support early in life results in severe cognitive, social, developmental, and health consequences throughout development (Bowlby, 1988; Gunnar, 2001; House, Landis, & Umberson, 1988; Holt-Lundstad, Smith, & Layton, 2010; Tottenham & Sheridan, 2010). However, although humans require close social bonds to survive and thrive (Bowlby, 1988; Taylor, 2010; Uchino, 2004) few have explored the experience of social connection—the positive, contented feelings associated with being close to others—or how individuals come to feel connected to those they love the most. Furthermore, little is known about the neurochemical mechanisms that help support social bonds, especially in humans.

According to the brain opioid theory of social attachment, endogenous opioids, specifically  $\mu$ -opioids, are thought to mediate the pleasant feelings stemming from social bonding and affiliation (Panksepp, 1998). More specifically, opioids have been proposed to underlie the affiliative, interpersonal feelings (e.g. warmth, affection) that come from social connection (Depue and Morrone-Strupinsky, 2005; Panksepp, 1998). Furthermore, the theory states that experiences of social loss or separation lead to reduced opioid activity thus leading to feelings of disconnection and separation distress. Although few studies have examined the role of opioids in human attachment relationships, data from animal models support the theory that opioids are involved in social bonding (e.g., Burkett et al, 2011; Kalin et al, 1988; Kalin et al, 1995; Keverne et al, 1989; Moles et al., 2004; Panksepp et al., 1980; Shayit et al., 2003; Schino & Troisi, 1992; Trezza et al, 2011).

Only a handful of studies have explored the effects of opioids on perceptions of social rewards and social attachment experiences in humans. With regard to the effect of opioids on social rewards, morphine (vs. naltrexone) leads to higher attractiveness ratings for the most attractive faces presented, suggesting that opioids can enhance ‘liking’ toward certain stimuli (Chelnokova et al., 2014). One early study (described in Depue and Morrone-Strupinsky, 2005 but not published on its own), examined the role of opioids in social attachment processes. Here, female participants were administered naltrexone (25mg) and placebo (separated by a 4-day period) and were asked to rate their feelings of connection in response to watching two separate movie clips: an affiliative movie clip of a couple giving birth to their first child and a neutral film clip of a nature scene. In line with the brain opioid theory of social attachment, naltrexone (vs. placebo) reduced the increases in warm, affectionate feelings to watching the affiliative clip (compared to the neutral clip) among those high in trait affiliation. Similarly, Schweiger and colleagues (2014) have recently shown that a 25mg dose of naltrexone (vs. placebo) reduced affiliative feelings (cozy, comforting, liked, secure) after an economic trust game. Furthermore, we have recently shown that naltrexone (vs. placebo) reduces feelings of connection both in the lab and out in the real world (Inagaki, Ray, Irwin, Way, & Eisenberger, 2016). Together, these results suggest that opioids may subserve feelings of connection.

Though not directly manipulating opioids, neuroimaging findings on close social bonds show that opioid-rich neural regions activate to cues of close others. Thus, reading loving messages

(vs. neutral messages) from close friends and family members activates the ventral striatum (VS), ventral tegmental area (VTA), pregenual (pACC) and dorsal anterior cingulate cortex (dACC); orbitofrontal cortex (OFC), and insula (Inagaki & Eisenberger, 2013), all regions known to be high in  $\mu$ -opioid receptors (Cross, Hille, & Slater, 1987; Jones et al., 1999; Panskepp & Bishop, 1981; Vanderschuren, Stein, Wiegant, & Van Ree, 1995; Willoch et al., 1999; Wise & Herkenham, 1982; Zubieta et al., 2001). Similarly, the VS, OFC, and VTA are more active when viewing images of close others (vs. strangers or acquaintances) such as one's own baby or romantic partner (Acevedo, Aron, Fisher, & Brown, 2012; Bartels & Zeki, 2004; Strathearn, Li, Fonagy, & Montague, 2008). Though not tested yet, it is possible that opioid antagonism may reduce activity in these affiliation-related neural regions.

Together, emerging evidence from humans and animals point to the possibility that  $\mu$ -opioids contribute to the experience of bonding and connecting with others, but few have explored the role of opioids in social bonding in humans. As such, the current study aims to test the brain opioid theory of social attachment to better understand the role of opioids in maintaining close social bonds.

## Study Objectives

This study will examine the role of opioids on social connection processes and more specifically, will explore the effect of blocking opioids on feelings of social connection and connection-related neural activity.

## Study Design & Methods

Overview: To assess the role of opioids in the experience of connecting with others, an opioid antagonist, naltrexone, will be administered in a randomized, double-blinded, placebo controlled design. Participants will attend a baseline session where they will complete trait measures in order to obtain baseline measures in feelings of connection. Participants will then be scheduled for an fMRI scan where they will be randomly assigned to a drug condition (naltrexone or placebo). During the scan, participants will complete a number of tasks designed to elicit feelings of social connection. After the scan, participants will complete self-report measures in order to assess the effect of opioid antagonism on perceptions of their social relationships.

Timeline and anticipated duration of study procedures:

1. Telephone Screening (15 minutes)
2. In-person visit #1 (Sennott Square): review and sign consent form, baseline questionnaires (60 minutes)
3. In-person visit #2 (Neuroscience Imaging Center): Experimental Session at fMRI scanner (3 hours)
  - 3a. Assignment to study drug, wait for peak effects (60 minutes)
  - 3b. fMRI scan (60 minutes)
  - 3c. post scan assessments and video recording (60 minutes)

Total time: 4 hours

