### IN-PERSON BASELINE VISIT #1:

Participants will review the consent form and be allowed to ask clarifications before giving consent to participate. Participants will then answer questions about their perceptions of their

social relationships, feelings over the past 24 hours, general health and health-related behaviors, and demographics. In addition, participants will be asked to complete a number of personality measures to establish a baseline for social interactions and feelings about relationships.

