#### **POST SCAN ASSESSMENTS:**

Outside of the scanner, participants will rate their feelings of connection (e.g. “How connected did reading the messages make you feel?”, “How warm did reading the messages make you feel?”, “How touched did reading the messages make you feel?”) to reading each set of messages. They will also complete the same physical symptoms checklist that they completed prior to taking the study drug and their perceptions of their close other from the picture task.

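### Perceptions of the pictured close others are rated only after the drug; a matching pre-drug rating used as a covariate would be a cheap gain in precision

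*Combined protocol and SAP*

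**What the plan says.** All references are to the combined protocol and SAP.

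- Study Design & Methods, overview: at baseline participants "complete trait measures in order to obtain baseline measures in feelings of connection". After the scan, "participants will complete self-report measures in order to assess the effect of opioid antagonism on perceptions of their social relationships".
- In-person baseline visit #1: questions cover perceptions of "social relationships, feelings over the past 24 hours, general health and health-related behaviors, and demographics", together with "personality measures to establish a baseline for social interactions and feelings about relationships". The people in the photographs are not mentioned.
- In-person visit #2: the only self-report listed before dosing is a physical symptoms checklist.
- fMRI scan, picture task: before the experimental session each participant supplies images of two people to whom they feel close.
- Post scan assessments: "Outside of the scanner, participants will rate their feelings of connection" for each set of messages. Two further items follow: "same physical symptoms checklist that they completed prior to taking the study drug and their perceptions of their close other from the picture task".
- Statistical Considerations: the primary outcomes include self-reported connection in response to both tasks. Self-report is compared between groups by independent samples t-tests, and no baseline covariate is named.

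**The concern.** The close-other rating is the only listed post-scan self-report tied to the picture task, and that task is part of the primary outcome. The documents do not say whether this rating is the picture-task connection outcome, but nothing else on the list could be.

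Participants choose their own two people, so ratings will plausibly differ between participants for reasons unrelated to the drug: a spouse of many years and a recent friend need not score alike. With no rating of the same people before dosing, this variation cannot be separated from the drug effect within a participant. It widens the confidence interval, and a chance imbalance between arms in prior closeness cannot be seen or adjusted for directly. At stake is precision on one self-report measure, not the validity of the comparison.

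**Working it through.** **Step 1. Set the listed assessments side by side.**

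| Measure | Listed before drug | Listed after drug |
|---|---|---|
| Physical symptoms checklist | Yes (visit #2) | Yes, same checklist |
| Message-connection ratings | No; they respond to the task | Yes |
| Perceptions of social relationships in general | Yes (visit #1) | Stated as a purpose in the overview; no instrument itemised |
| Perceptions of the pictured close other | No | Yes |

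The last row is the gap. The absence of a pre-drug message rating is expected, because that rating is a response to the task. A view of a person known to the participant exists before the task and could be rated beforehand.

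**Step 2. Effect of a matching baseline on residual variance.** The documents give no figure to reproduce: no sample size, power, effect size or correlation is stated for this rating. With a linear baseline covariate that correlates r with the outcome within arms, residual variance is (1 − r²) times the unadjusted variance.

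- r = 0.3: 1 − 0.09 = 0.91, a fall of 9%
- r = 0.5: 1 − 0.25 = 0.75, a fall of 25%
- r = 0.7: 1 − 0.49 = 0.51, a fall of 49%

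**Step 3. What this means for the detectable difference (illustration).** The Results section reports the two-group imaging comparison with 75 degrees of freedom, so N = 75 + 2 = 77. Assume the same N for the rating, an equal split (38.5 per arm), two-sided alpha of 0.05, 80% power and a normal approximation. In units of the unadjusted SD:

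d = √(1 − r²) × √(2/38.5) × (1.960 + 0.842)

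- No covariate: 1 × 0.228 × 2.802 = 0.64
- r = 0.3: 0.61
- r = 0.5: 0.55
- r = 0.7: 0.46

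**Step 4. Compare with the covariates already collected.** The fair comparator is not only an unadjusted test. Suppose the visit #1 relationship and trait measures together correlate 0.3 with the post-drug rating (assumed), and add nothing once a matching baseline is in the model (also assumed). Residual variance then starts at 0.91 instead of 1:

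- matching r = 0.5: 1 − 0.75/0.91 = 18% further reduction
- matching r = 0.7: 1 − 0.51/0.91 = 44% further reduction

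The extra gain shrinks as the existing measures predict the rating better.

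**The case against.** The strongest case against the point is that nothing here is invalid. The trial is randomized with parallel groups, no change score is planned, and a post-drug comparison is unbiased without any baseline. Perceptions of the close other are not named as a primary outcome, and no reported result rests on them. The correlation is assumed, and 77 is inferred from imaging degrees of freedom, not from a count of these ratings. All of this stands, and it limits the point to precision.

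A reader might infer more. The documents do not support the following:

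- *That pre- and post-drug assessments in general do not pair up.* The symptoms checklist is explicitly the same before and after the drug, and the message ratings need no counterpart.
- *That perceptions of social relationships have no post-drug data.* The overview states a post-scan self-report for this purpose. The close-other item may be how it is carried out. The post-scan section is also not exhaustive: the timeline schedules a video recording that it does not mention. What is missing is the name of an instrument.
- *That adjustment cannot help without the matching item.* A covariate need only correlate with the outcome, so the visit #1 measures can serve, though only in part.
- *That the past-24-hour feelings should have been repeated.* Nothing makes them a drug outcome. The visit timeline puts the post-scan hour roughly two to three hours after dosing, so most of a 24-hour recall would describe time before the drug.

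**Conclusion.** The point holds as a cheap improvement, not as a flaw that threatens a conclusion. One post-drug measure, the only self-report listed for the picture task, has no listed matching baseline, although the people concerned are identified before dosing. For r between 0.5 and 0.7, the loss amounts to a detectable difference of 0.64 SD where 0.55 to 0.46 SD would have been attainable. If the visit #1 measures are used as covariates, less is lost.

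This rests on the assumed correlation, on equal arms totalling 77, and on reading the visit lists as covering what is asked about the pictured people. If a rating of those people is already among the unnamed visit #1 questionnaires, only the analysis change remains.

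**What to change.** - **In-person baseline visit #1, or visit #2 before dosing:** have participants rate the two people whose photographs are used, with the same items as after the scan. Visit #1 puts more time between the two ratings but requires the people to be named by then. At visit #2 the photographs are already in hand, but the earlier answers are fresher.
- **Post scan assessments:** name the items, and say whether one or both people are rated and how the ratings are combined.
- **Statistical Considerations:** analyse the post-drug close-other rating by ANCOVA, with drug as the factor and the matching pre-drug rating as covariate, in place of the unadjusted t-test. State whether this rating is the picture-task connection outcome. The visit #1 relationship and trait measures can stay as they are.

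The cost is a few minutes of questionnaire at an existing visit, one degree of freedom in the model, and protocol wording. The downside is that participants may anchor to their earlier answers, which could slightly shrink a drug difference.

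The document already reports results, so the added rating can help only a repeat or extension. For data in hand, adjustment for the visit #1 measures is the available substitute, and it should be labelled as decided after the plan.

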### IN-PERSON BASELINE VISIT #1:

Participants will review the consent form and be allowed to ask clarifications before giving consent to participate. Participants will then answer questions about their perceptions of their

social relationships, feelings over the past 24 hours, general health and health-related behaviors, and demographics. In addition, participants will be asked to complete a number of personality measures to establish a baseline for social interactions and feelings about relationships.

#### IN-PERSON VISIT #2:

On the day of the study, participants will arrive at the Magnetic Resonance Research Center (MRRC) where they will complete a urine drug test to test for the presence of opiates and other drugs, a urine pregnancy test (if female) and complete a baseline physical symptoms checklist. A positive urine test for either drugs or pregnancy will result in the withdrawal of the participant from the study.

To ensure safety for an MRI scan, participants will undergo a two-step safety screening procedure with the MRI technician. First, a written screening form is completed during a face-to-face interview with the participant and the technologist. Once the participant has passed the written screening, then visual screening is performed by the technologist to identify and eliminate any contraindicated objects on the participant's body or clothing. Participants will then be randomly assigned to receive either 50mg of oral naltrexone or placebo.

Details on drug randomization and study drug blind methods: (1) Randomization: An individual unassociated with the main study will randomly assign participants to drug A or drug B on the day of the scheduled scanning session by using a block randomization method. This will ensure that there are equal numbers of men and women assigned to each drug condition. This individual will not have access to any of the data or any information about the participant except for their gender and age. It will be necessary for the person in charge of randomization to know the gender and age of the participant so that they may keep the two conditions balanced. (2) Study Drug Blind: The PI ([name]), study coordinator, any trained research assistant's, and the participants will all be blinded during the study, thereby maintaining the double-blind. Only the study physician, [name], and the individual who performs the randomization will be unblinded. The PI will be told which drug is A and which is B at the end of data collection. Finally, the drug and placebo will be packaged into identical capsules so that the pills look identical to the experimenters.

#### fMRI SCAN:

Approximately 60 minutes after taking the study drug, when naltrexone is known to show peak effects (Lee et al, 1988), participants will complete an fMRI scan. During this time they will be asked to either lie still inside the bore of the magnet while brain scans are acquired or be asked to perform the following tasks inside the MRI machine:

Messages task: Participants will read a variety of messages from friends and family members, and from strangers. Messages will be presented in a block design with 3 messages presented per block, separated by 6-second rest periods. Participants will read both positive and neutral messages from close others and as further control conditions, positive and neutral messages from strangers.

Picture task: Prior to attending their experimental session, participants will provide the study coordinator with 2 images of 2 different people with whom they feel close. Once in the scanner,

participants will view images of their close others as well as gender, race, and age-matched strangers as a control condition. In between blocks of pictures, participants will complete mental arithmetic.

#### **POST SCAN ASSESSMENTS:**

Outside of the scanner, participants will rate their feelings of connection (e.g. “How connected did reading the messages make you feel?”, “How warm did reading the messages make you feel?”, “How touched did reading the messages make you feel?”) to reading each set of messages. They will also complete the same physical symptoms checklist that they completed prior to taking the study drug and their perceptions of their close other from the picture task.

### **Eligibility Criteria**

Inclusion criteria require participants to be in good health, between the ages of 18 and 35, fluent in English, be willing to provide digital photographs of their close others (for the picture scanner task) and identify 6-8 friends and family members who might be willing to be contacted in regards to the current research study (for the messages scanner task). In addition, participants must be right-handed and free of metal (for the fMRI scan).

Participants will be excluded for the following:

Self-reported current or past diagnoses of physical or mental illness.

Score on the Patient Health Questionnaire (depressive symptoms) above a 9

Positive urine drug test (for THC, Opiates, Cocaine, AMP, and mAMP)

Positive urine pregnancy test

Use of any prescription medication, except for birth control

Use of any over-the-counter medications on the day of the fMRI session and 24 hours after the fMRI session

Self-reported problems with liver functioning, including hepatitis or liver failure

Difficulty swallowing or taking pills

fMRI specific exclusions:

BMI greater than 35 or weight greater than 400 lbs (the weight limit of the fMRI scanner)

Claustrophobia

Nonremovable metal in the body

### **Statistical Considerations**

Primary outcomes: Neural activity and self-reported feelings of connection in response to the messages task and the picture-viewing task.

Neuroimaging outcome: The imaging data will be analyzed using SPM8 (Wellcome Department of Cognitive Neurology, Institute of Neurology, London, UK). Images for each participant will be realigned to correct for head motion, normalized into a standard stereotactic space, and smoothed with an 8mm Gaussian kernel, full width at half maximum, to increase signal-to-noise ratio. The imaging tasks are all block designs and therefore we will use a boxcar function convolved with a canonical hemodynamic response function. For each participant, each block

type will be modeled separately (e.g. viewing images of a close other will be modeled separately from viewing images of a stranger). After the task is modeled for each participant, planned comparisons will be computed as linear contrasts to investigate neural activity separately during each of the conditions compared to baseline (fixation crosshairs) and each condition compared to its respective control condition (e.g. images of close other vs. images of stranger). Random effects analyses of the group will be computed using the contrast images generated for each participant.

To assess between-group differences in the effect of naltrexone vs. placebo on neural responses to the different tasks, we will conduct two kinds of analyses for each task. First, based on a priori hypotheses regarding the effect of naltrexone on affiliation-related neural responses, we will conduct region-of-interest (ROI) analyses, using structurally-defined ROIs, to examine between-group differences in neural activity in these pre-specified neural regions ( $p < .05$ , corrected). For the task where participants read messages from their loved ones, ROIs of the VS and mid-insula, have been created (with the PickAtlas toolbox) using the automated anatomical atlas (AAL; Tzourio-Mazoyer et al., 2002), and will be examined to see if average neural activity in these regions differs between naltrexone and placebo participants in response to the messages. Similarly, for the picture-viewing task, ROIs of the left and right VS will be analyzed in the same way (these have also been structurally defined previously; Inagaki et al., 2015). Second, to more fully investigate the specific neural regions that are differentially activated as a function of naltrexone (beyond the predicted ROIs), we will conduct whole-brain between-group analyses to see which neural regions differ in activity among participants exposed to naltrexone vs. placebo ( $p < .001$ , 10 voxels).

Feelings of social connection: To assess between-group differences in the effect of naltrexone vs. placebo on self-reported feelings of connection in response to the scanner tasks, we will conduct independent samples t-tests.

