## Results for primary outcomes

Effect of Naltrexone on Neural Activity to Messages task: To examine the effect of naltrexone on neural activity to the social warmth task, analyses were constrained to the a-priori defined VS and MI mask. VS and MI activity was greater to messages from close others than strangers (*left*  $t(76)=6.138$ ,  $p < .001$ ; *right*  $t(76)=4.493$ ,  $p < .001$ ). Naltrexone, however, reduced VS and MI activity to the social warmth task as compared to placebo (*left*  $t(75)=1.859$ ,  $p=.034$ ; *right*  $t(75)=2.198$ ,  $p=.016$ ).

Effect of Naltrexone on Feelings of Social Connection to Messages task: The effect of drug on feelings of social connection to the messages task was in the expected direction, but did not reach statistical significance ( $p > .10$ ).

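### Four primary components have no error control across them and no rule for how many must succeed; under a post hoc Holm rule the reported messages-task brain effect does not survive

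*Combined protocol and SAP*

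**What the plan says.** All references are to the combined protocol and SAP. Statistical Considerations opens with "Primary outcomes: Neural activity and self-reported feelings of connection in response to the messages task and the picture-viewing task". The components are joined without ranking.

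For the imaging outcome the plan says "we will conduct two kinds of analyses for each task": ROI comparisons, then a whole-brain search that goes beyond the predicted regions. The ROI part examines "between-group differences in neural activity in these pre-specified neural regions ( $p < .05$ , corrected". Neither the correction method nor the family it covers is given. The wording is non-directional: messages-task activity "will be examined to see if average neural activity in these regions differs between naltrexone and placebo participants in response to the messages". The messages-task regions are the ventral striatum (VS) and mid-insula; the picture-task regions are the left and right VS.

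For ratings the whole specification is "self-reported feelings of connection in response to the scanner tasks, we will conduct independent samples t-tests". No alpha, sidedness or adjustment is stated. Post Scan Assessments lists several rating items (connected, warm, touched) and defines no composite.

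Results for primary outcomes gives messages-task drug effects on brain activity of t(75)=1.859, p=.034 (left) and t(75)=2.198, p=.016 (right). The messages-task rating effect "was in the expected direction, but did not reach statistical significance", with p above .10. No picture-task result appears there.

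**The concern.** With several primary components, the reader needs to know in advance whether one positive component supports a claim or all must be positive, and how the error rate is held across them. The plan answers neither question. Its only correction belongs to the ROI tests, so it does not cover brain and ratings together, and it is not said to cover both tasks.

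This matters because the results are split. If any one component may carry a claim, the brain finding on the messages task is a positive primary result, but one drawn from a family whose error rate was not controlled. If all four were required, no adjustment would be needed, and the study would have failed on the messages ratings alone. The plan does not choose between these readings, and two of the four components are not reported.

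**Working it through.** The documents give no sample size calculation, power or trial-wide alpha, so there is no design figure to reproduce. The checkable figures are the two reported brain p-values.

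**1. Reported p-values.** Inputs are t=1.859 and t=2.198 on 75 degrees of freedom, from Results for primary outcomes. One-sided p = P(T75 > t); two-sided p is twice that.

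| Side | t(75) | Printed p | One-sided | Two-sided |
|---|---|---|---|---|
| Left | 1.859 | .034 | .0335 | .067 |
| Right | 2.198 | .016 | .0155 | .031 |

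The printed values are one-sided. The left-side result misses 5% two-sided.

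**2. Number of components.** 2 outcome types × 2 tasks = 4. The whole-brain search is not counted.

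**3. Chance of at least one false positive.** Assumptions: no true effect on any component, each tested at two-sided 5%, any one able to carry a claim.

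- Independent: 1 − 0.95^4 = 18.5%.
- Equal correlation ρ, with c = 1.96: 1 − ∫ [Φ((c − √ρ·u)/√(1−ρ)) − Φ((−c − √ρ·u)/√(1−ρ))]^4 φ(u) du. This gives 17.4% at ρ = 0.3, 15.6% at 0.5, 13.0% at 0.7 and 9.4% at 0.9.
- If the ROI correction spans both tasks, there are three 5% families (brain, messages ratings, picture ratings): 1 − 0.95^3 = 14.3% if independent, 12.5% at ρ = 0.5, 8.4% at 0.9.

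The documents give no correlation, so ρ is shown as a range. All these figures exceed 5%.

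**4. What a family rule would do.** Bonferroni at .05/4 = .0125 each gives 1 − (1 − .0125)^4 = 4.9% if independent, and at most 5.0% otherwise. Holm has the same guarantee with thresholds, from the smallest p upward, of .05/4 = .0125, .05/3 = .0167, .05/2 = .025 and .05.

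**5. Holm applied to the messages-task brain result.**

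- Take the more favourable side: .031 two-sided.
- The messages rating p is above .10, whichever sidedness was used, so it comes later in the ordering.
- The brain component therefore cannot be last of four. The latest place it can hold is third, with threshold .025.
- .031 > .025, so it fails whatever the two unreported picture-task p-values are. Its Holm-adjusted p is at least 2 × .031 = .062.
- Taking the smaller side is generous. With Bonferroni over left and right, the component p is 2 × .031 = .062, which exceeds even the last threshold of .05.

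**The case against.** The strongest reply is that the plan never says any one component is enough. The components are joined by a plain conjunction, Study Objectives describes an exploration of feelings and of neural activity, and the results section reports each outcome separately. It says openly that the ratings were not significant and makes no overall claim of success. All of that stands. What remains is that the documents call these outcomes primary and report a drug effect on one of them, with no rule saying what that supports.

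Three stronger readings are tempting and are not supported.

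- A reader might infer that the trial-wide error rate simply is 16–19%. The documents give no alpha for the ratings, no correlation and no any-one-wins rule, and the ROI correction may span both tasks. The rate is conditional and can be lower.
- A reader might instead count six separate tests (four ROI, two rating) and quote 1 − 0.95^6 = 26.5%. That ignores the correction the plan does state for the ROI tests.
- A reader might set the printed .016 against Holm's .0125 and .0167 and conclude that it could pass at the second step. That compares a one-sided p for one hemisphere with two-sided thresholds for a whole component. The like-for-like figure is .031 at best.

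It is also fair to say that a single Holm family is one defensible choice among several, and that adopting it now is retrospective. The second point is met by labelling it so.

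**Conclusion.** The concern holds in conditional form. The plan names four primary components, controls error at most within the ROI tests, and sets no success rule. If each component is tested at two-sided 5% and any one may carry a claim, the chance of at least one false positive is up to about 19%, and it stays above 5% in every scenario computed.

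The effect on the reported findings does not depend on the assumed correlation. Under Holm over four components at two-sided 5%, the messages-task brain result does not survive, and the messages rating component is not shown. This rests on the printed t statistics, on two-sided testing (consistent with the plan's non-directional wording), and on the rating p above .10 being that component's p-value. It does not show that naltrexone has no effect on brain activity, only that the evidence does not meet a family-wise 5% standard.

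**What to change.** - **Statistical Considerations:** state that the four components form one family tested by Holm at two-sided 5%, and that claims are limited to components that survive. Label the rule post hoc, since results are known. Do not promote one component to sole primary now.
- **One p-value per component:** state a reduction rule that does not pick the best result. For example, use Bonferroni over the left and right ROI tests for brain, and a t-test on the mean of the rating items for ratings.
- **Results for primary outcomes:** replace .034 and .016 with the two-sided .067 and .031. Report all four components, including the picture task, with Holm-adjusted two-sided p-values. Describe the messages-task brain effect as not surviving family-wise correction, and the messages rating component as not shown.

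The cost is wording plus a short reanalysis of data already collected. It cannot be completed from the documents alone: the analysts must supply the picture-task p-values and the exact rating p-values. The downside is a stricter threshold, under which the reported brain effect becomes nominal or exploratory.
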